Clinical response to treatment with alogliptin or alogliptin FDCs will be evaluated based on HbA1c levels. The HbA1c level goal for the patient will be collected at baseline, when determined as part of standard clinical practice. Response will be defined as (1) HbA1c level change from baseline; (2) HbA1c levels reduction to the goal of <7%; and (3) HbA1c reduction >0.3% with no tolerability findings (hypoglycemic event, or weight gain $\geq 5\%$). The HbA1c levels will be obtained from any assessments performed as per standard clinical practice. No study-specific measurements will be performed. If multiple HbA1c levels are available, then the assessment closest to the visit time point will be used.

Data on the use of alogliptin or alogliptin FDCs will include start date, dose, and end date. Information will also be collected on any additional T2DM treatment, both added in combination to alogliptin or due to switching treatment from alogliptin or alogliptin FDCs to another T2DM treatment.

Incidence of newly diagnosed co-morbidities and complications will be collected.

Body weight will be obtained from any assessments performed as per standard clinical practice. No study-specific measurements will be performed.

Healthcare resources utilization will be assessed by number of hospitalizations (including length of stay during each hospitalization, reason, and urgency [urgent/not urgent]), emergency room visits, and physician office visits.

Safety will be assessed by ADRs, SAEs, and AEs of special interest.

Study Drug:

This is an observational study. Alogliptin or alogliptin FDCs will be prescribed per routine clinical practice.

Sample Size:

Approximate 1199 patients are planned to be enrolled, not less than 1027, and no more than 1383.

Statistical Methods:

This study is observational and epidemiological methods will be employed for data analyses. Statistical analysis will be performed using SAS[®] software (SAS Institute, Inc., Cary, North Carolina) Version 9.2 or later. Continuous variables will be summarized using the mean, the standard deviation, median, 25th percentile, 75th percentile, minimum value, and maximum value. Categorical variables will be summarized using frequency counts and percentages. Data will be listed in data listings. A flow chart according to CONSORT guidelines will capture the

patient enrollment and the analysis sets at each analysis. No formal significance testing will be performed.

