Adverse reactions reported in $\geq 4\%$ of patients treated with alogliptin 25 mg and more frequently than in patients who received placebo are upper respiratory tract infections, nasopharyngitis, and headache; other common adverse reactions included abdominal pain, gastroesophageal reflux disease, pruritus, and rash. Additional adverse reactions that have been spontaneously reported post-marketing are hypersensitivity reactions including

anaphylaxis, angioedema, urticaria, and severe cutaneous reactions including Stevens-Johnson syndrome. In addition, acute pancreatitis and hepatic dysfunction (including fulminant hepatic failure) have also been reported post-marketing.

The EXAMINE study was conducted in 5380 patients (2679 receiving placebo and 2701 receiving alogliptin) to assess potentially elevated cardiovascular risk related to alogliptin through a composite primary endpoint including death from cardiovascular causes, non-fatal myocardial infarction, and non-fatal stroke (White et al 2013). The results of this study showed that the composite primary endpoint occurred at similar rates in both treatment groups after a median exposure of 18 months (alogliptin: 11.3%; placebo: 11.8%; hazard ratio: 0.96; upper boundary of the 1-sided repeated confidence interval [CI]: 1.16; $p < 0.001$ for non-inferiority; $p = 0.32$ for superiority).

This study is designed to observe alogliptin and alogliptin with pioglitazone and with metformin (alogliptin FDCs) (depends on the different drugs available in China and Hong Kong) in real-life settings a non-interventional manner. Patients will be enrolled after they and their healthcare provider make the decision to employ alogliptin or alogliptin FDCs for the treatment of T2DM. Therefore, alogliptin or alogliptin FDCs will be prescribed independent of the inclusion of the patient in the study. All treatment decisions will be based on the prescribing physician's current clinical practice.

2 Study Objectives

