4.2 Withdrawal of Patients From the Study

The duration of the study is defined for each patient as the date signed written informed consent is provided through to the last study visit. Patients may withdraw their consent at any time and for any reason without prejudice to their future medical care by the investigator or at the study site.

Patients switching treatment from alogliptin or alogliptin FDCs to another T2DM treatment will be followed until the end of the study.

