### **8.4.2. Secondary Efficacy Analyses**

The secondary HbA1c or fasting blood glucose outcomes (HbA1c clinical response rates) will be summarized by treatment as descriptive statistics and incidence rates.

If multiple HbA1c levels are available, then the assessment closest to the visit time point will be used. Clinical response rates: incidence rates of responders. The following definitions of response will be used: (1) HbA1c level reduction to the goals of <7.0%. (2) HbA1c reduction >0.3% with no tolerability findings (hypoglycemic event, or weight gain  $\geq 5\%$ ).

- HbA1c level change from baseline in subgroups with different clinical characteristics. It is proposed to use multifactorial regression model to determine factors related to effect of alogliptin and its FDCs on HbA1c level dynamics. Change from baseline in HbA1c level on alogliptin or its FDCs therapy (V3) in subgroups with different clinical characteristics will be summarized using relevant descriptive statistics and analyzed using Multiple Linear Regression with following predictors: prior therapy of DM, sex, age, cardiovascular risk group, therapy type (monotherapy or combined therapy), baseline BMI, initial glycemic control.

In addition, change from baseline in HbA1c level will be assessed and evaluated using mixed model repeated measures (MMRM) methodology. The multiple visits for each patient will be incorporated as repeated measures within each patient. Visit will be treated as a categorical predictor and baseline HbA1c level will be included as a covariate. An appropriate covariance structure will be selected to provide estimates (Least Square Means) of change from Baseline and to perform statistical analysis at Visit 3. If the unstructured covariance matrix results in a lack of convergence, the heterogeneous Toeplitz covariance structure, followed by the heterogeneous autoregressive covariance structure, followed by compound symmetry will be used. The dose-response trend hypothesis test will be conducted using the appropriate contrast statement for a linear (ordinal dose) trend. In addition, Least Squares Means, the associated standard errors and 95% confidence intervals will be displayed by each individual dose group.

[figure not shown]
- Proportion (%) of patients with diabetes mellitus type 2 whose HbA1c<7.0% will be described and presented in summary tables using absolute frequencies and percentages as well as 95% confidence intervals;

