### **8.5.1. Extent of Exposure**

Below by-subject listing will be provided:

- Initial study treatment dosing, including initial treatment, dosage, frequency, time of administration, and ongoing etc. information.
- Study treatment adjustment, including adjustment start/end date, type, action taken, dosage, frequency, unit, primary reason for action taken, AE/ADR name (if available).

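### A dose-response trend test is ordered in a plan that rules out significance testing, with dose group undefined and no dose term named in the model

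*SAP*

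**What the plan says.** On testing, the protocol says "No formal significance testing will be performed", in both the abstract and section 7.8. SAP 8.1 repeats the sentence. SAP 5, the section for the statistical hypothesis, reads NA.

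On dose, SAP 8.4.2 adds a mixed model for repeated measures (MMRM) of the HbA1c change and then says "The dose-response trend hypothesis test will be conducted using the appropriate contrast statement for a linear (ordinal dose) trend". It continues: "Least Squares Means, the associated standard errors and 95% confidence intervals will be displayed by each individual dose group". Protocol 7.8.2 carries the same two instructions. The model terms given in the SAP are: "Visit will be treated as a categorical predictor and baseline HbA1c level will be included as a covariate".

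On what is recorded, SAP 8.5.1 lists two dosing records per patient. One is "Initial study treatment dosing, including initial treatment, dosage, frequency, time of administration, and ongoing etc. information". The other is "Study treatment adjustment, including adjustment start/end date, type, action taken, dosage, frequency, unit, primary reason for action taken". The products observed are "alogliptin and alogliptin with pioglitazone and with metformin (alogliptin FDCs) (depends on the different drugs available in China and Hong Kong"). Protocol 4.2 adds that "Patients switching treatment from alogliptin or alogliptin FDCs to another T2DM treatment will be followed until the end of the study".

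**The concern.** The two instructions pull against each other. One rules out significance tests for the study; the other orders a named hypothesis test and gives no null hypothesis, alpha or sidedness. The analyst has to decide whether a trend p-value belongs in the report.

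The test is also not fully specified. The analyst would have to supply the dose variable, the order of the groups, the place of the fixed-dose combinations on that order, and the dose terms in the model. Each choice can change the result, and the visible plan fixes none of them.

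What is at stake is interpretation. A p-value labelled dose-response invites the reading that more drug lowers HbA1c more. In this design the physician sets the dose (Protocol 5), and dose escalation or reduction during follow-up is itself a secondary endpoint (SAP 4.2).

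**Working it through.** **1. Testing policy against the ordered test.** Three places bar formal testing: the protocol abstract, Protocol 7.8 and SAP 8.1. Two order a hypothesis test: Protocol 7.8.2 and SAP 8.4.2. None mentions the other or makes an exception. The only alpha in either document, 0.05 two-sided, belongs to the precision calculation in Protocol 7.5 and SAP 6. It sets a confidence level there, not a test.

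**2. Can the named model give the requested output?** With the named terms the model is

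change at visit j = visit effect j + b × baseline HbA1c + error.

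This gives one least-squares mean per visit for the whole cohort. A linear dose contrast has the form Σ c_k × (effect of dose group k), and the named terms contain no effect of dose group k. Least-squares means by dose group need the same missing factor. Because the analysis is aimed at Visit 3, a dose-by-visit term is needed too; without one, the dose differences are forced to be equal at Visits 2 and 3. The seven predictors of the separate linear regression in SAP 8.4.2 do not include dose. The later repeated-measures models refer only to clinical characteristics.

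**3. What a dose group could be.** SAP 8.5.1 supports at least two definitions.

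- *Initial dose.* The physician chose it in view of the patient, so group differences mix dose with the reasons for choosing it (confounding by indication).
- *A later dose.* It may have been changed because of earlier HbA1c, so response may decide group membership.

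Under neither definition does a trend across groups isolate an effect of dose.

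**4. Precision of a by-dose display, all on one basis (unadjusted paired change).** Inputs from Protocol 7.5 and SAP 6: SD 0.65, baseline-to-V3 correlation 0.35, confidence level 95%.

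SD of change = 0.65 × √(2 × (1 − 0.35)) = 0.65 × √1.3 = 0.741.

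The plan's own figure comes first. The smallest n for which the half-width is at most 0.05 with 90% probability, given that the interval covers the true mean, is 899 pairs (actual probability 0.904), as stated. Dropout: 899 / 0.75 = 1198.7, so 1199, as stated.

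For one group of m patients with V3 data, half-width = t(0.975, m − 1) × 0.741 / √m. The values of m are assumed, because the SAP gives no actual count.

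| m (assumed) | t | Half-width (percentage points) |
|---|---|---|
| 15 | 2.145 | 0.41 |
| 25 | 2.064 | 0.31 |
| 50 | 2.010 | 0.21 |
| 100 | 1.984 | 0.15 |

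These are about three to eight times the planned 0.05 for the whole cohort. They leave out the 90% assurance built into the 0.05. Without it, 899 pairs give 1.963 × 0.741 / √899 = 0.049, so the comparison hardly changes.

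**The case against.** *Formal may mean confirmatory.* On that reading a nominal exploratory p-value breaks no rule, and the analyst is not forced to disobey either instruction. This is plausible and cannot be excluded. But neither document says it, and a test for which the SAP gives the hypothesis as NA has nothing to support it. Naming the test as an exploratory exception would settle the wording; it would not make the p-value interpretable as a dose effect.

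*The dose factor is implied.* By-dose means cannot be produced without one, and SAP 8.4.2 does not say that visit and baseline are the only terms. That stands: it is a gap in drafting, not proof that the analysis is impossible. The gap still leaves open which dose is used and whether it interacts with visit.

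*Redaction.* The exploratory sections are blacked out and might define dose groups. The point is therefore limited to visible text, although this analysis is specified among the secondary ones.

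*Stronger readings that a reader might infer.* One is that the trend test would be biased against the higher dose, or would reject too often by a known amount. The documents do not say that groups come from a later dose or that poor responders are escalated, and they give no split of starting doses, so neither the size nor the direction of any bias can be derived. Another is that grouping by initial dose removes the bias. It avoids grouping on earlier response, but the initial dose is still chosen by the physician.

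**Conclusion.** The point holds for this secondary analysis. The plan both bars formal testing and orders a hypothesis test, does not reconcile the two, and leaves the dose factor unnamed and dose group undefined in visible text. Because dose is physician-chosen and changeable, a trend p-value would not support a dose-response conclusion.

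The conflict needs no figure. The half-widths of 0.41 to 0.15 percentage points show only how imprecise by-dose results could be. They rest on the plan's SD and correlation and on assumed group sizes; SAP 9.1 says that enrolment fell far short of plan but gives no number.

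A reader might infer that the study's main result is compromised. It is not: the primary analysis in SAP 8.4.1 is descriptive, and the sample size is built on the precision of the overall change, which reproduces. The correction should be made, but nothing outside this analysis depends on it.

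**What to change.** 1. Delete the trend hypothesis test from SAP 8.4.2 and record this as a departure from Protocol 7.8.2. Keep the by-dose least-squares means, with n and 95% confidence intervals, labelled descriptive and non-causal.
2. For that display, define dose group from the initial dosing record in SAP 8.5.1, keep different products and strengths separate, and add dose group and dose group by visit to the MMRM. Without a trend test, no ordering of the fixed-dose combinations is needed.
3. State whether HbA1c values measured after a switch away from alogliptin count in this display. The endpoint in SAP 4.1 and the analyses in SAP 8.4.1 and 8.4.2 refer to change while on alogliptin or its combinations, whereas Protocol 4.2 keeps switchers in follow-up. The rule must be reconciled with both.

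Cost: SAP wording, two model terms and one recorded departure; no new data, and no change to the primary analysis or sample size. There will be no trend p-value, the initial dose is not necessarily the dose taken at V3, and keeping products and strengths apart may leave some groups small.

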The HbA1c outcomes (change of HbA1c from baseline to different follow-up period, and HbA1c clinical response rates) will be summarized as descriptive statistics and incidence rates. Secondary study outcome - change from baseline in glycosylated hemoglobin level on alogliptin or its FDCs therapy in subgroups with different clinical characteristics, is proposed to use multifactorial regression model to determine factors related to effect of alogliptin or its FDCs.

Overall and center-specific proportion of participants remaining on alogliptin at the end of the follow-up period will be summarized as frequency and percentages. Treatment patterns will be summarized at each follow-up time and overall at 6 months as descriptive statistics and incidence rates. Alternatively, Kaplan-Meier curves may be used. Receipt of another T2DM treatment will be summarized at each time period and overall at 6 months as incidence rates. Similar analyses will be performed for other time to event endpoints.

Other endpoints (rates of comorbidities and complications, changes in body weight, number of hospitalizations and healthcare resources utilization, and length of hospitalization) will be summarized by descriptive statistics and incidence rates at each time period and for the overall duration.

All safety endpoints (ADRs, SAEs, and AESIs) will be summarized.

Date of Protocol:

1st April 2016

List of Abbreviations

Abbreviation	Definition
ADR	adverse drug reaction
AE	adverse event
AESI	adverse event of special interest
CFR	Code of Federal Regulations
CI	confidence interval
CRO	contract research organization
DPP-4	dipeptidyl peptidase-4
eCRF	electronic case report form
FDC	fixed-dose combination
GPP	Good Pharmacoepidemiology Practices
HbA1c	glycated hemoglobin
ICF	informed consent form
IEC	independent ethics committee
IRB	institutional review board
MedDRA	Medical Dictionary for Regulatory Activities
SAE	serious adverse event
T2DM	type 2 diabetes mellitus

1 Introduction

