7.2 Secondary Endpoints

The secondary endpoints related to real-world clinical response to alogliptin or alogliptin FDCs are the following:

- Clinical response rates: incidence rates of responders. The following definitions of response will be used as secondary endpoints:
 - Change from baseline in HbA1c level on alogliptin or its FDCs therapy in subgroups with different clinical characteristics(V3).
 - HbA1c levels reduction to the goals of <7.0%(V3).
 - HbA1c reduction >0.3% with no tolerability findings (hypoglycemic event, or weight gain $\geq 5\%$) (V3).
 - To evaluate the effect of alogliptin and its FDCs on fasting blood glucose dynamics in patients with diabetes mellitus type 2 over time (V1-V2-V3).
- To evaluate the effect of alogliptin or alogliptin FDCs on glycosylated hemoglobin (HbA1c) level dynamics in patients with diabetes mellitus type 2 in dependence on clinical characteristics(V1-V2-V3).
- ADRs, SAEs, and AESIs.

The secondary endpoints related to alogliptin or alogliptin FDCs utilization patterns are the following:

- Percentage of patients who remain on treatment with alogliptin or alogliptin FDCs(V2-V3).
- Time to alogliptin or alogliptin FDCs dose escalation or dose reduction(V2-V3).

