- Change from baseline in glycosylated hemoglobin (HbA1c) level on alogliptin or its FDCs therapy over time (V1-V2-V3) will be summarized using relevant descriptive statistics and analyzed with mixed model with repeated measures using clinical characteristics as independent factors;
- All safety data will be analysed on the safety population. Prior to analysis, adverse drug reactions will be coded using MedDRA.
 - Incidence and characteristic of adverse drug reactions will be described and presented in summary tables using absolute frequencies and percentages as well as 95% confidence intervals;
 - Evaluation of AEs, including the AEs, will consist of the determination of total number of AEs, total number of patients with AEs and the number of AEs requiring discontinuation of the study treatment. The incidence and severity of all AEs will be summarized by body system. Treatment discontinuation due to AEs will be tabulated
 - AEs reported in the study as well as AEs reported directly to authorities and to Takeda International Drug Safety and not captured in the study database will be extracted from the overall safety database and the study database and listed or tabulated in the final report in the standard way of presenting such data in a Periodic Safety Update Report (PSUR).
- Proportion (%) of patients who remain on Alogliptin or its FDCs treatment (V2-V3) and information of dose escalation or reduction will be described and presented in summary tables using absolute frequencies and percentages as well as 95% confidence intervals

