### 4.2. Secondary Endpoint

The secondary endpoints related to real-world clinical response to alogliptin or alogliptin FDCs are the following:

- Clinical response rates: incidence rates of responders. The following definitions of response will be used as secondary endpoints:
  - Change from baseline in HbA1c level on alogliptin or its FDCs therapy in subgroups with different clinical characteristics (V3).
  - HbA1c levels reduction to the goals of <7.0% (V3).
  - HbA1c reduction >0.3% with no tolerability findings (hypoglycemic event, or weight gain  $\geq 5\%$ ) (V3).
  - To evaluate the effect of alogliptin and its FDCs on fasting blood glucose dynamics in patients with diabetes mellitus type 2 over time (V1-V2-V3).
- To evaluate the effect of alogliptin or alogliptin FDCs on glycosylated hemoglobin (HbA1c) level dynamics in patients with diabetes mellitus type 2 in dependence on clinical characteristics (V1-V2-V3).
- ADRs, SAEs, and AESIs.

The secondary endpoints related to alogliptin or alogliptin FDCs utilization patterns are the following:

- Percentage of patients who remain on treatment with alogliptin or alogliptin FDCs (V2-V3).
- Time to alogliptin or alogliptin FDCs dose escalation or dose reduction (V2-V3).

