## 7. ANALYSIS POPULATION

### 7.1. Analysis Sets

The analysis will be performed on the complete set of patients enrolled in the study. Subgroup analyses will be carried out on the subgroups defined in Section 4.3.

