- Proportion (%) of patients with diabetes mellitus type 2 who decrease in HbA1c > 0.3% with no tolerability findings (hypoglycemic event, or weight gain  $\geq 5\%$ ) over time will be described and presented in summary tables using absolute frequencies and percentages as well as 95% confidence intervals;
- Change from baseline in fasting plasma glucose level on alogliptin or its FDCs therapy over time (V1-V2-V3) will be summarized using relevant descriptive statistics and analyzed with mixed model with repeated measures using clinical characteristics as independent factors;
- Change from baseline in HbA1c level on alogliptin or its FDCs therapy over time (V1-V2-V3) will be summarized using relevant descriptive statistics and analyzed with mixed model with repeated measures using clinical characteristics as independent factors;
- Proportion (%) of patients who remain on Alogliptin or its FDCs treatment (V2-V3) and information of dose escalation or reduction (V2-V3) will be described and presented in summary tables using absolute frequencies and percentages as well as 95% confidence intervals.

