## **9.3. Impact of Limited Visit**

The study termination will lead to missing visit of V2 or V3, and efficacy results might not be obvious.

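### Time to dose escalation or reduction is a secondary endpoint, but the SAP plans only percentages for it, with no censoring rule and no stated denominator after early termination

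*SAP*

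**What the plan says.** Both documents define the endpoint as a time. Protocol 7.2 has "Time to alogliptin or alogliptin FDCs dose escalation or dose reduction(V2-V3" and SAP 4.2 has "Time to alogliptin or alogliptin FDCs dose escalation or dose reduction (V2-V3", each as a secondary utilization endpoint.

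Both methods sections then treat it as a proportion. Protocol 7.8.2 says that "information of dose escalation or reduction will be described and presented in summary tables using absolute frequencies and percentages", and SAP 8.4.2 says that "information of dose escalation or reduction (V2-V3) will be described and presented in summary tables using absolute frequencies and percentages". Each adds 95% confidence intervals. Neither gives a time origin, an event definition, a censoring rule or a denominator.

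The protocol abstract (Statistical Methods) goes further. It plans descriptive statistics and incidence rates for treatment patterns at each follow-up time and overall at 6 months. It then adds "Alternatively, Kaplan-Meier curves may be used" and, shortly after, "Similar analyses will be performed for other time to event endpoints". Protocol 7.8 sets the index date as the first day on alogliptin and leaves details to the SAP. SAP 8.4.2 takes up neither.

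Four other SAP statements matter here:
- Section 7.1: "The analysis will be performed on the complete set of patients enrolled in the study".
- Section 8.2.1: missing data are not imputed.
- Section 9.2: early termination widens confidence intervals but does not affect point estimates.
- Section 9.3: "The study termination will lead to missing visit of V2 or V3".

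**The concern.** A percentage with a dose change does not estimate a time to dose change. If SAP 8.4.2 is followed as written, the study reports no result for the endpoint it defined.

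With complete 6-month follow-up this would matter less, because the percentage would at least be a 6-month risk. The sponsor stopped the study early, however, so patients will have been observed for different lengths of time. A crude percentage takes no account of that. Its meaning then depends on how patients without V2 or V3 are counted, and the SAP does not say. The same data could give clearly different dose-change rates according to a choice made at programming.

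**Working it through.** **Plan's own figure.** There is none for this endpoint. The sample-size tables (for example 899 pairs, and 899/0.75 = 1199 enrolled) concern the HbA1c change. They reproduce, but they do not bear on this point.

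**Inputs.** The 6-month maximum follow-up comes from SAP 3. The documents give neither a dose-change rate nor the share of patients cut short, so these are assumed:
- true 6-month probability of a dose change p = 20% (10% as a second case), with constant hazard;
- share cut short c = 25%, 50% or 75%;
- cut-off times uniform over 0 to 6 months and unrelated to the risk of a dose change.

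**Step 1: risk seen in patients cut short.** The hazard is λ = −ln(0.8)/6, so 6λ = 0.2231. Averaged over a uniform cut-off time, the probability of having seen the event is

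q = 1 − (1 − e^(−6λ))/(6λ) = 1 − 0.20/0.2231 = 0.1037.

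**Step 2: three possible denominators.**
- A, all enrolled, with patients not seen to change counted as no change: (1 − c)p + cq.
- B, only patients who reached V3: p.
- C, patients who reached V3 plus any patient with an earlier event: [(1 − c)p + cq] / [(1 − c) + cq].

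For c = 25%, A = 0.75 × 0.20 + 0.25 × 0.1037 = 0.1759, and C = 0.1759/(0.75 + 0.0259) = 0.2267.

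| Share cut short | A: all enrolled | B: reached V3 | C: reached V3 or earlier event |
|---|---|---|---|
| 25% | 17.6% | 20% | 22.7% |
| 50% | 15.2% | 20% | 27.5% |
| 75% | 12.8% | 20% | 39.0% |

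The relative error under A is about −12%, −24% and −36%. With p = 10%, q = 1 − 0.10/0.1054 = 0.0509, and A gives 8.8%, 7.5% and 6.3%, a similar relative error. If patients cut short contribute no follow-up at all, A becomes (1 − c)p: 15%, 10% and 5% for a true 20%.

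**Step 3: check by simulation.** With 200,000 simulated patients and a true 20%, A was 17.7%, 15.2% and 12.9%, and C was 22.8%, 27.5% and 39.3%. The Kaplan-Meier estimate at 6 months was 20.1%, 20.0% and 20.1%. Under these assumptions, censoring removes the distortion.

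**The case against.** The strongest reply is that the direction of bias is not fixed. A reader might infer that the planned percentages must be too low. The documents do not establish that. SAP 8.4.2 gives no denominator, and its V2-V3 label could mean visit-based counts. Counting an unseen patient as having no dose change could also be seen as the imputation that SAP 8.2.1 rules out. SAP 7.1 favours the enrolled set, but only as a general statement. This objection stands: downward bias is conditional on denominator A.

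A reader might also infer that no time-to-event method was ever foreseen. That is too strong. The protocol abstract permits Kaplan-Meier curves and extends similar analyses to other time-to-event endpoints. But the permission is optional, it never appeared in Protocol 7.8.2, and the SAP section for this endpoint does not adopt it.

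A third inference would be that persistence on treatment is analysed wrongly too. This is not supported. That endpoint is defined as a percentage, so a percentage matches it. Time to switching or discontinuation is listed as exploratory in SAP 4.3, and the exploratory methods (Protocol 7.8.3, SAP 8.4.3) are redacted, so nothing can be said to be missing there. What remains is that the denominator for the percentage remaining on treatment is also unstated. Persistence could be overstated or understated, depending on whether unseen patients are counted as remaining or not.

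Finally, this is a descriptive secondary endpoint in a study without hypothesis tests, and dose adjustments are listed by subject under SAP 8.5.1. That limits the consequence. A listing is still not an estimate.

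**Conclusion.** The point holds in this form. The endpoint is a time, and the visible SAP analysis of it yields no time estimate and does not handle unequal follow-up after early termination. This rests on unredacted text and needs no assumption.

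The numerical effect on the crude percentage is illustrative only. Under the assumed inputs, a true 20% reads between 12.8% and 17.6% on the enrolled set, exactly 20% among patients who reached V3, and between 22.7% and 39.0% if earlier events are added to the V3 patients. The lack of bias among V3 patients, and in Kaplan-Meier, requires that being cut short is unrelated to dose changes. That is plausible for a sponsor's termination and less certain for loss to follow-up. The actual size cannot be derived from the documents.

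The general statement in SAP 9.2 that termination does not affect point estimates is therefore not safe for this endpoint. The primary HbA1c analysis is outside this point.

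**What to change.** In SAP 8.4.2:

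1. Define the time origin as the index date in Protocol 7.8. Define two events: first dose escalation and first dose reduction.
2. Estimate each by Kaplan-Meier or cumulative incidence, and report 3- and 6-month estimates with 95% confidence intervals.
3. Censor at last contact or the administrative end of the study, whichever comes first.
4. State how alogliptin discontinuation and death are handled, as competing events or as censoring. Protocol 4.2 keeps patients who switch treatment in follow-up. Without a rule they would stay at risk of an alogliptin dose change that can no longer occur, and the estimate would itself be too low.
5. Keep the crude percentages as supportive, each with a stated denominator. Do the same for the percentage remaining on treatment.

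In SAP 9.2, qualify the statement on point estimates so that it does not cover cumulative percentages under truncated follow-up.

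The cost is SAP wording and one extra table or figure. No new data are needed: start date, dose and end date are collected under Protocol 6.1.5, and adjustment dates are already listed under SAP 8.5.1. No significance test is added.
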